## Experimental Design Schema

### Dose Escalation Schema

NSC Dose Level	Initial Enrollment	If 1 DLT, Add'l Enrollment	NSC Dose	NSC and Irinotecan a Administration			
				Week	1	2	3
-1	3	3	$2.5 \times 10^7$	X*		**	
1 b	3	3	$5 \times 10^7$	X		**	
2 c	3	3	$5 \times 10^7$	X		X	
3	3	3	$1 \times 10^8$	X		X	
4 d	3	3	$1.5 \times 10^8$	X		X	
Expansion Cohort e	8		MTD/MFD	X		X	

\* "X" denotes treatment weeks for NSCs and irinotecan. NSCs are administered intracranially on Day 1 and 15, followed by intravenous irinotecan, two days later, on Days 3 and 17 of a 28 day cycle.

\*\*Patients on dose levels 1 and -1 will only receive 1 dose of NSCs, but they will continue to receive irinotecan every 2 weeks as long as they are tolerating it well, and there is no evidence of tumor progression.

**a**Dose schedule A, B, and C will be the NSC dose schema in combination with an irinotecan dose of 180mg/m^2, 150 mg/m^2, or 125 mg/ m^2, respectively. We will start with irinotecan dose schedule A, de-escalating through doses B and C in order as necessary.

**b** The starting NSC dose level is dose level 1. The first 6 study participants will undergo intracerebral microdialysis to measure levels of irinotecan and NSC-mediated SN-38 production in the brain. Since the dose of NSCs remains the same for dose level 1 and 2, all of these first 6 study patients would receive the same dose of NSCs and irinotecan when undergoing intracerebral microdialysis, even allowing for escalation to dose level 2.

**c** Starting with dose level 2, a Rickham reservoir/catheter system will be placed at the time of surgery for administering repeat doses of NSCs.

**d** Six patients will be treated on the maximum tolerated dose(MTD), or, if the MTD is not reached, at the maximum feasible dose (MFD). Since it is anticipated that the MTD/MFD will be 150 million NSCs (dose level 4), the 6 patients who will be treated on dose level 4 will undergo intracerebral microdialysis and be counted as part of the expansion cohort.

**e** An expansion cohort of 8 patients will be treated at the MTD or MFD to gain more experience with the tolerability of this treatment regimen. These patients will also undergo intracerebral microdialysis to assess how much SN-38 is produced by highest dose of NSCs and evaluate the biologic activity of the NSCs by directly measuring how much the addition of NSCs to treatment with irinotecan increases intracerebral levels of SN-38. As such, 4 patients in the expansion cohort will undergo intracerebral microdialysis after receiving NSCs on the day of surgery followed 2 days later by IV irinotecan, and the other 4 patients in this cohort will not receive NSC administration on the day of surgery. Instead they will be given IV irinotecan 2 days after surgery and dialysate samples will be collected from them to determine how much SN-38 is present in the brain from treatment with

IV irinotecan alone. These 4 patients will then receive their first dose of NSCs through the Rickham on day 15 of cycle 1 followed by irinotecan on day 17.

### Simplified Treatment Schema for Cycle 1

#### Day 1

Tumor resection or biopsy is performed.

hCE1m6-NSCs are administered intracranially.^

A Rickham catheter is placed (except in patients on dose levels 1 or -1).

The first 6 study patients and those in the expansion cohort: microdialysis catheter(s) is/are placed, and a post-operative CT scan is obtained to confirm correct placement.

^Four participants in the expansion cohort will not receive Day 1 NSCs; they will initiate NSC administration on Day 15.

#### Day 3

Irinotecan is administered intravenously.

Patients undergoing intracerebral microdialysis: serial dialysate and bloodsamples are collected.

#### Day 15

hCE1m6-NSCs are administered intracranially via the Rickham catheter.\*

Blood is drawn for immunologic correlative studies.\*

\* Patients in dose level 1 or -1 will not receive NSCs on Day 15, and blood samples for immunologic correlative studies will be drawn on Day 17 when these patients return to clinic to receive irinotecan.

#### Day 17

Irinotecan is administered intravenously.

## Protocol Synopsis

Protocol Title:
A Phase I Study of Intracranially administered Carboxylesterase-Expressing Neural Stem Cells in Combination with Intravenous Irinotecan in Patients with Recurrent High Grade Gliomas.
Brief Protocol Title for the Lay Public (if applicable):
A Phase I study of Neural Stem Cells and Irinotecan in Patients with High-Grade Gliomas
Study Phase:
Phase I
Participating Sites:
City of Hope
Rationale for this Study:

High-grade gliomas are difficult to treat due to their highly invasive nature and relative resistance to chemotherapy and radiation. Human neural stem cells (NSCs), modified to express a therapeutic transgene, hold great promise for glioma therapy due to their inherent tumor-tropic properties, enabling their use as vehicles for delivering chemotherapy directly to infiltrating glioma cells. This NSC-mediated delivery approach has the potential to overcome obstacles that limited gene therapy efficacy in the past and minimize off target toxicities of current treatment approaches.
 
Data from animal models have demonstrated the safety and efficacy of NSCs for tracking to invasive tumor cells as well as to distant micro-tumor foci and delivering therapeutic gene products to tumor cells. In our first-in-human pilot study of cytosine deaminase (CD)-expressing NSCs given in combination with oral 5-fluorocytosine (5-FC), we showed that 1 dose of CD-expressing NSCs followed by a 7 day course of 5-FC in recurrent high-grade glioma patients is safe and feasible. With intracerebral microdialysis, we documented proof-of-concept—that the NSCs converted the prodrug 5-FC to its active metabolite 5-FU locally in the brain. Results of immunologic correlative studies documented no findings of NSC immunogenicity after first exposure. Magnetic resonance imaging (MRI) of iron-labeled NSCs showed preliminary evidence of NSCs migrating away from the injection sites, and autopsy results from 2 study patients showed evidence that NSCs had traveled to distant sites of tumor in the brain.
 
This well characterized, v-myc-immortalized, clonal, human fetal NSC line has been further modified by adenoviral transduction to secrete a highly active modified human form (hCE1m6) of carboxylesterase (CE) for efficient conversion of irinotecan to its more potent metabolite, SN-38. We hypothesize that in patients with recurrent high-grade gliomas, CE-secreting NSCs will distribute throughout the primary tumor site as well as co-localize with infiltrating tumor cells within 2 days of administration. Study patients will then be treated with intravenously administered irinotecan. The CE-secreting NSCs will locally convert irinotecan to SN-38, thereby generating concentrated cytotoxicity at sites of tumor in the brain.

Objectives:

**Primary Objectives:**

To define the recommended phase II dose (RP2D) of intracranially administered hCE1m6-NSCs in combination with intravenous irinotecan in patients with recurrent high grade glioma. The RP2D will be based on the maximum-tolerated dose (MTD), or if the MTD is not reached, the maximum feasible dose (MFD), and the full toxicity profile including toxicities associated with repeat doses of NSCs.

**Secondary Objectives:**

- To describe the relationship between hCE1m6-NSC dose and SN-38 concentrations in brain interstitium.
- To characterize the relationship between intracerebral and systemic concentrations of irinotecan and SN-38.
- To investigate the biologic activity of hCE1m6 NSCs by comparing SN-38 concentrations in the brain after treatment with hCE1m6 NSCs and irinotecan versus irinotecan alone.
- To assess for possible development of adenovirally transduced NSC immunogenicity after first exposure and with repeat doses of NSCs.
- To describe the clinical benefit (defined as stable disease, partial response, or complete response) in patients who receive treatment with repeat cycles of NSCs and irinotecan.
- To determine, at time of autopsy, the fate of the NSCs.

**Study Design:**

This phase I clinical trial will define the recommended phase II dosing (RP2D) based on dose-limiting toxicities (DLTs) and the full toxicity profile of the combination of hCE1m6-NSCs and irinotecan using a standard "3 + 3" dose escalation schema in patients with recurrent highgrade gliomas who are undergoing a debulking craniotomy or stereotactic brain biopsy. Except for dose levels 1 and -1, where only 1 dose of NSCs will be given (these patients can continue to receive treatment with irinotecan every 2 weeks), NSCs will be administered intracranially on days 1 and 15, and irinotecan will be given intravenously 2 days later, on days 3 and 17 of a 28 day cycle. With subsequent cohorts of patients, the NSC dose will be increased as tolerated, but the dose of irinotecan will remain the same unless DLTs occur that necessitate lowering the dose of irinotecan. A Rickham reservoir/catheter system will be placed at the time of surgery for delivering repeat doses of NSCs intracranially. MRIs and PET/CT scans of the brain will be performed at least every two months (at the end of every even cycle of study treatment to evaluate response).

Three doses of NSCs will be assessed. The starting dose will be  $5 \times 10^7$  NSCs, which was well-tolerated in the first-in-human study of CD-expressing NSCs. Due to volume limitations for intracerebral administration, the highest dose of NSCs to be tested will be  $1.5 \times 10^8$  cells. Study participants will receive repeat cycles of study treatment (dose level 1 and -1 patients will only receive repeat doses of irinotecan) as long as they are tolerating the treatment well, and there is no evidence of progressive disease.

An important secondary objective of this study will be to determine the biologic activity of the hCE1m6-NSCs by measuring concentrations of SN-38 in brain interstitium using intracerebral microdialysis. The first 6 patients to enroll in the study and the last 8 patients in the expansion cohort will undergo microdialysis to collect data regarding intracerebral levels of irinotecan and SN-38 when patients are treated with the lowest and highest NSC doses. Please note, the same dose of NSCs ( $5 \times 10^7$ ) is given to patients on dose levels 1 and 2, so whether the first 6 patients are all treated on dose level 1 or the first 3 dose level 1 and the next 3 on dose level 2, they will all receive the same dose of NSCs.

Once the maximum tolerated dose of the combination therapy has been determined, or, if the maximum tolerated dose is not met, the maximum feasible dose, patients in the expansion cohort will undergo intracerebral microdialysis to investigate if treatment with a higher dose of NSCs results in more SN-38 in the brain and to directly determine how much the addition of NSCs to treatment with irinotecan increases

intracerebral levels of SN-38. As such, 4 patients in the expansion cohort will undergo intracerebral microdialysis after receiving NSCs at the time of surgery followed 2 days later by IV irinotecan, but the other 4 patients in this cohort will not receive NSCs on the day of surgery. Instead they will be given IV irinotecan 2 days after surgery, and dialysate samples will be collected from them to determine how much SN-38 is present in the brain from treatment with IV irinotecan alone. These 4 patients will then receive their first dose of NSCs through the Rickham on day 15 of cycle 1 followed by irinotecan on day 17. Another key secondary objective will be to assess for possible development of immune responses to these allogeneic, adenovirally transduced NSCs. Serial blood samples will be collected during treatment cycles to assess for the possible development of T cell and antibody responses to the NSCs and/or cell surface-expressed adenoviral proteins, and we will follow adenoviral antibody titers.

Other secondary objectives include describing the clinical benefit in patients who receive treatment with repeat cycles of NSCs and irinotecan by obtaining MRIs and PET/CT scans of the brain at least every two months to assess response and, when feasible, determining at time of autopsy the fate of the NSCs.

#### Endpoints:

**Safety and Feasibility:** 1) For Dose Escalation: Dose Limiting Toxicities

2) Toxicity Profile: All Attributable Toxicities

**Pharmacokinetics:** Cmax and AUC of irinotecan and SN-38 in dialysate and plasma.

**Immunogenicity:** Evaluate patient blood samples for the development of T cell responses and antibodies against the NSCs and/or cell surface-expressed adenoviral proteins using TcR V $\beta$  spectratyping, CD 107 degranulation assays, and flow cytometry. Measure patients' serial adenoviral antibody titers.

**Clinical Benefit:** Tumor response based on brain MRI and PET/CT scan results.

#### Determine the Fate of the NSCs: NSC Persistence

#### Sample Size:

The anticipated sample size is 29 patients: minimum=6; maximum=53 (allowing for 42 patients for dose escalation through 5 possible dose levels of NSCs and 3 dose schedules of irinotecan, estimating ~3 patients to replace unevaluable/ineligible patients and an additional 8 patients for the expansion cohort).

#### Estimated Duration of the Study:

36 months to complete accrual

#### Summary of Subject Eligibility Criteria:

##### **Inclusion Criteria**

- Patient has a prior, histologically-confirmed, diagnosis of a grade III or IV glioma, or has a prior, histologically-confirmed, diagnosis of a grade II glioma and now has radiographic findings consistent with a high-grade glioma (grade III or IV).
- Imaging studies show evidence of recurrent tumor(s). If a patient is going to be enrolled to dose level two or higher, the patient must have a component of supratentorial disease (so as to enable placement of a Rickham reservoir/catheter) that is amenable to resection or biopsy.

- Patient must be in need of a craniotomy for tumor resection or a stereotactic brain biopsy for the purpose of diagnosis or differentiating between tumor progression versus treatment-induced effects following radiation therapy ± chemotherapy.
- Patient's high-grade glioma has recurred or progressed after prior treatment with brain radiation and temozolomide.
- Patient must be at least 18 years old and less than 70 years old.
- Patient has a Karnofsky Performance Status of  $\geq 70\%$ .
- No limit to prior number of therapies.

#### Exclusion Criteria

- Patient is homozygous for the UGT 1A1\*28 allele and/or has Gilbert's disease.
- Patient must not be taking any hepatic enzyme-inducing anticonvulsants (phenytoin, carbamazepine, phenobarbital, primidone, oxcarbazepine) for at least 2 weeks prior to enrollment.
- Patients have anti-HLA antibodies specific for HLA class I antigens expressed by the hCE1m6-NSCs.
- Patient is taking flucytosine.

#### Investigational Product Dosage and Administration:

#### Dose Escalation Schema

NSC Dose Level	Initial Enrollment	If 1 DLT, Add'l Enrollment	NSC Dose	NSC and Irinotecan a Administration			
				Week	1	2	3
-1	3	3	$2.5 \times 10^7$	X*		**	
1 b	3	3	$5 \times 10^7$	X		**	
2 c	3	3	$5 \times 10^7$	X		X	
3	3	3	$1 \times 10^8$	X		X	
4 d	3	3	$1.5 \times 10^8$	X		X	
Expansion Cohort e	8		MTD/MFD	X		X	

\* "X" denotes treatment weeks for NSCs and irinotecan. NSCs are administered on Day 1, and irinotecan, 180 mg/m^2/dose, is administered two days post-NSCs on Day 3 of each treatment week. The length of a treatment cycle is 28 days.

\*\*Patients on dose levels 1 and -1 will only receive 1 dose of NSCs, but they will continue to receive irinotecan every 2 weeks as long as they are tolerating it well, and there is no evidence of tumor progression.

aDose schedule A, B, and C will be the NSC dose schema in combination with an irinotecan dose of 180mg/m^2, 150 mg/m^2, or 125 mg/m^2, respectively. We will start with irinotecan dose schedule A, de-escalating through doses B and C in order as necessary.

b The first 6 study participants will undergo intracerebral microdialysis to measure levels of irinotecan and NSC-mediated SN-38 production in the brain. Since the dose of NSCs remains the same for dose level 1 and 2, and microdialysis will be performed only with the first dose of irinotecan, all of these first 6 study patients would

receive the same dose of NSCs and irinotecan when undergoing intracerebral microdialysis, even allowing for escalation to dose level 2.

**c** Starting with dose level 2, a Rickham reservoir/catheter system will be placed at the time of surgery for administering repeat doses of NSCs.

**d** Six patients will be treated on at the maximum tolerated dose (MTD), or, if the MTD is not reached, at the maximum feasible dose (MFD). Since it is anticipated that the MTD/MFD will be 150 million NSCs (dose level 4), the 6 patients who will be treated on dose level 4 will undergo intracerebral microdialysis and be counted as part of the expansion cohort.

**e** An expansion cohort of 8 patients will be treated at the MTD or MFD to gain more experience with the tolerability of this treatment regimen. These patients will undergo intracerebral microdialysis to assess how much SN-38 is produced by highest dose of NSCs and evaluate the biologic activity of the NSCs by directly measuring how much the addition of NSCs to treatment with irinotecan increases intracerebral levels of SN-38. As such, 4 patients in the expansion cohort will undergo intracerebral microdialysis after receiving NSCs on the day of surgery followed 2 days later by IV irinotecan, and the other 4 patients in this cohort will not receive NSC administration on the day of surgery. Instead they will be given IV irinotecan 2 days after surgery and dialysate samples will be collected from them to determine how much SN-38 is present in the brain from treatment with IV irinotecan alone. These 4 patients will then receive their first dose of NSCs through the Rickham on day 15 of cycle 1 followed by irinotecan on day 17.

#### Clinical Observations and Tests to be Performed:

##### **Collection of dialysate and blood samples to determine the neuropharmacokinetics of irinotecan and SN-38.**

*Only in patients who undergo intracerebral microdialysis*—On day 3 of cycle 1, dialysate samples will be collected every 60 minutes for 24 hours and then every 3 hours for the next 24 hours. Blood samples will be drawn just prior to the start of the irinotecan infusion and at 90 minutes (just prior to the end of the infusion), and then at 30 minutes, 1, 2, 4, 8, 24, and 48 hours after the end of the infusion.

**Collection of blood samples for immunologic correlative studies:** To assess for possible development of T cell and antibody responses to the NSCs and/or cell surface-expressed adenoviral proteins, adenoviral vector (Ad5) antibody titers and total adenoviral antibody titers, as well as presence of the NSCs and hCE1m6 in the systemic circulation, blood samples will be drawn: prior to surgery, on day 15 of cycle 1 (prior to administering the 2nd dose of NSCs), days 1 and 15 of cycle 2, and then only on day 15 of subsequent treatment cycles.

**Collection of blood samples to perform replication competent retrovirus (RCR) testing as part of long-term follow-up:** Prior to surgery, at 3 months, 6 months, 1 year, and annually thereafter.

**Brain MRIs and PET/CT scans to assess response:** At least every 2 months.

#### Statistical Considerations:

Tables will be created to summarize all toxicities and side effects by dose, course, organ severity (by NCI CTCAE version4.0), and attribution. Rates and associated 95% Clopper Pearson confidence limits will be estimated for the DLTsand clinical benefit at the RP2D.Descriptive statistics will be provided for study patient demographics.

Pharmacokinetic data from patients who undergo intracerebral microdialysis will be summarized using descriptive statistics and graphical methods.The biologic activity of the hCE1m6-NSCs, based on comparison of microdialysis SN38 PK data from patients receiving NSCs + irinotecan vs patient s receiving irinotecan alone will be assessed using a one-sided two-sample t test.Regression analysis will be used to assess the relationship between hCE1m6-NSC dose and SN-38 concentrations in brain interstitium using microdialysis data from the patientstreated with the initial NSC dose (n=6) and from the patients in the expansion cohort treated with the highest NSC dose (n=4).Other secondary objectives include assessing for possible development of NSC immunogenicity after first and repeat exposuresand—when feasible—evaluating the fate of the NSCs at autopsy. These results will be summarized using descriptive statistics and graphical methods.

Sponsor:

City of Hope

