#### Concomitant medications

2. Use of CYP3A4 **inducers** including hepatic enzyme-inducing anticonvulsants (phenytoin, fosphenytoin, carbamazepine, phenobarbital, primidone, oxcarbazepine) within 2 weeks prior to start of study treatment (See Table 6.2).
3. Use of **moderate to strong** CYP3A4 **inhibitors** within 2 weeks prior to start of study treatment (See Table 6.2).
4. Use of drugs known to **inhibit** UGT1A1, such as Atazanir, Gemfibrozil, Indinavir, or Ketoconazole, within 2 weeks prior to start of study treatment).
5. Co-medication that may interfere with study results; e.g. immuno-suppressive agents other than corticosteroids, such as systemic cyclosporine and tacrolimus. Consult Principal Investigator for questions, including necessary washout period for the specific drug.
6. Flucytosine within 2 weeks prior to start of study treatment.
7. Use of herbal medications.
8. Current use (or planned use during the treatment period) of other investigational agents, or biological, chemotherapy, radiation or other anti-tumor therapy. See Inclusion Criterion 12, for required washout periods from these therapies.

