#### 6.1.1 REQUIRED Peri- and post-operative Prophylaxis

---

Levetiracetem (Keppra)—or another anticonvulsant that does not cause significant induction of hepatic metabolic enzymes, such as lacosamide or valproic acid—will be administered to all study patients. Those who have never had a seizure will start taking levetiracetam within 1 week prior to surgery and continue taking the anti-seizure medication for 4 weeks after craniotomy or biopsy.

Peri-operative antibiotics, corticosteroids, and deep vein thrombosis prophylaxis will be used according to the standard of care for the surgical procedure.

For participants with microdialysis catheters, prophylactic antibiotic use will continue as long as the microdialysis catheter(s) remains in place.

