#### **6.1.6 REQUIRED Management of Possible Immune Response to the NSCs**

Participants who develop a grade 2 or higher Immune Response to NSCs, will take dexamethasone to a maximum dose of 4 mg twice daily until symptoms resolve to  $\leq$  Grade 1. For participants continuing to receive NSCs, dexamethasone should continue at a dose determined by the treating investigator and per consultation with the principal investigator. For participants no longer receiving NSC administration may continue dexamethasone at the discretion of the treating investigator and per consultation with the principal investigator.

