#### 7.1.7 Criteria for First Administration of Irinotecan

For Cycle 1 Day 3 irinotecan administration, the participant must have recovered well from any immediate post-operative effects **and** requires no more than 16 mg/day of dexamethasone. Otherwise the participant will be removed from treatment. Criteria found in 7.2.4 also apply.

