- l. Inclusion/exclusion criteria. Source documentation providing investigator's confirmation that patient has met all eligibility criteria must be available prior to registration. In addition, source documentation by neurosurgeon that (a) a physical connection between the post-resection tumor cavity and cerebral ventricles is not anticipated, (b) a gross total resection is not anticipated, (c) the prospective participant is able to undergo neurosurgery, and (d) documentation that patient "needs a biopsy/craniotomy" is needed.
- m. Histology confirmation for to be performed by COH pathologist.
- n. Real-time histology confirmation to occur during surgery on fresh frozen section. See section 8.1 for pathology criteria. If confirmation of high grade glioma not obtained, all further study procedures will cease.
- o. Vital signs: Weight, heart rate, blood pressure, respiration rate, temp. Height required only at baseline. KPS not required at Day 2 and 3. See Appendix A for KPS scale.
- p. Participants no longer receiving NSCs (e.g. Dose Levels 1 and -1) may have their Day 15 assessments performed on Day 17, prior to irinotecan dosing.

- q. KPS and vital status only. Vital signs and Neuro-Physical exam are not required.
- r. Adverse events experienced by participants will be collected and recorded from signing of informed consent document up to 30 days of the last dose of study medication. The period for collection and recording of AEs is extended for participants with ongoing “reportable” adverse events that are related to study agent. Adverse event reporting begins for events that occur on Day 1 (day of neurosurgery).
- s. The only concomitant medication that needs to be documented in the case report form is whether the patient is taking dexamethasone (or another corticosteroid), and if so, what the dose is.
- t. For HLA testing, collect blood in 1 red top tube. Maintain at room temperature. Bring samples to COH Histocompatibility Laboratory.
- u. Participants who have already undergone UGT1A1 genotyping may use those results and do not the procedure repeated.

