#### 15.1.6 Analysis Plan:

---

Tables will be created to summarize all toxicities and side effects by dose, course, organ severity (by NCI CTCAE version 4.0), and attribution. Rates and associated 95% Clopper Pearson confidence limits will be estimated for DLTs and clinical benefit at the RP2D. Descriptive statistics will be provided for study patient demographics.

Pharmacokinetic data from patients who undergo intracerebral microdialysis will be summarized using descriptive statistics and graphical methods. The biologic activity of the hCE1m6-NSCs, based on comparison of microdialysis SN38 PK data from patients receiving NSCs + irinotecan vs patients receiving irinotecan alone, will be assessed using a one-sided two-sample t test. Regression analysis will be used to assess the relationship between hCE1m6-NSC dose and SN-38 concentrations in brain interstitium using microdialysis data from the patients treated with the initial NSC dose (n=6) and from the patients in the expansion cohort treated with the highest NSC dose (n=4). Other secondary objectives include assessing for possible development of NSC immunogenicity after first and repeat exposures, and—when feasible—evaluating the fate of the NSCs at autopsy. These results will be summarized using descriptive statistics and graphical methods.

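### The immunogenicity summary does not use the corticosteroid dose already recorded, so a negative or falling result drawn on steroid could not be told apart from true absence of a response

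*Combined protocol and SAP*

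**What the plan says.** **Analysis.** The Analysis Plan in Section 15 introduces the objective with "Other secondary objectives include assessing for possible development of NSC immunogenicity after first and repeat exposures" and then says "These results will be summarized using descriptive statistics and graphical methods". The Statistical Considerations in the synopsis match. The assay descriptions in Section 12 (T cell responses, antibody responses, adenoviral titers) do not mention corticosteroids.

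**Permitted exposure.** Exclusion criterion 5 bars co-medication that could interfere with study results, giving as its example "immuno-suppressive agents other than corticosteroids, such as systemic cyclosporine and tacrolimus". Section 6.2 repeats the exemption for the treatment phase. Section 6.1.1 states: "Peri-operative antibiotics, corticosteroids, and deep vein thrombosis prophylaxis will be used according to the standard of care". For the first irinotecan dose, on Cycle 1 Day 3, a participant must be one who "requires no more than 16 mg/day of dexamethasone".

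**Steroid as treatment of an NSC reaction.** Under Section 6.1.6, participants with a grade 2 or higher immune response "will take dexamethasone to a maximum dose of 4 mg twice daily until symptoms resolve" to grade 1 or less. Table 7.2.4 lets NSC dosing resume after a grade 2 reaction with dexamethasone continuing. After a grade 3 or 4 reaction, study treatment stops if an immune response is considered at least possible.

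**Data collected.** Footnote s of Table 10 states: "The only concomitant medication that needs to be documented in the case report form is whether the patient is taking dexamethasone (or another corticosteroid". Its dose is recorded too. Footnote ii builds that dose into the tumor response assessment.

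**The concern.** The protocol treats immunosuppression as something that can distort its results, and it prescribes dexamethasone to treat the very reaction that the immune assays are meant to detect. It takes steroid dose into account for tumor response but not for immunogenicity.

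The synopsis calls possible immune responses a key secondary objective. The background section on NSC immunogenicity says it is unknown whether responses to repeated exposure will limit the clinical use of these cells, and that this trial will look into it. If results are shown without steroid dose, a flat or falling course over repeat doses has two explanations that a reader cannot separate: no immune response, or a response dampened by dexamethasone. Repeat-dose samples are the most exposed, because a patient with a grade 2 reaction may be re-dosed while still on dexamethasone.

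**Working it through.** The plan gives no response rate, responder definition, sample size or power for immunogenicity, so there is no figure to reproduce. The check is mainly a comparison of provisions.

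1. **When samples are drawn.** Section 12 lists pre-surgery, Cycle 1 Day 15, Cycle 2 Days 1 and 15, then Day 15 of later cycles.
2. **Whether steroid is possible at those draws.** Yes. Corticosteroids are permitted throughout, and no dose limit is stated for any sampling day. The 16 mg/day figure applies to the first irinotecan dose on Cycle 1 Day 3, when no routine immunology sample is drawn. It says nothing about the dose at a draw.
3. **Whether steroid can be linked to a reaction.** Yes, for grade 2 reactions under Table 7.2.4. Later routine T cell and antibody samples from these patients can be drawn on dexamethasone.
4. **Whether the comparators remove the problem.** No. Each patient's pre- and post-treatment samples are compared, and antibody shifts are also judged against a panel of normal sera. Neither comparison accounts for the patient's steroid dose at the draw. If the dose changes between draws, within-patient change can be distorted in either direction.
5. **Whether the needed data exist.** Yes. Corticosteroid use and dose are on the case report form.

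**Illustration on assumed values.** Let p be the true share of responders, f the share of patients on steroid at sampling, and s the chance that a response is detected on steroid. With one assessment per patient:

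P(at least one detected) = 1 − (1 − p(1 − f + f·s))^n

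| n | p | no masking | f = 0.5, s = 0.5 | f = 0.8, s = 0.25 |
|---|---|---|---|---|
| 6 | 0.25 | 0.822 | 0.712 | 0.469 |
| 14 | 0.15 | 0.897 | 0.812 | 0.579 |
| 29 | 0.15 | 0.991 | 0.969 | 0.834 |

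For n = 14 and f = s = 0.5, the effective rate is 0.15 × (0.5 + 0.25) = 0.1125, and 1 − 0.8875^14 = 0.812. For f = 0.8 and s = 0.25 it is 0.15 × (0.2 + 0.2) = 0.06, and 1 − 0.94^14 = 0.579.

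The values of n and p are borrowed from the Sample Size section, where 6 with 0.25 and 14 with 0.15 refer to toxicity and 29 is the anticipated total. None is an immunogenicity assumption of the plan, and f and s are not in the documents at all.

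**A contradiction found on the way.** Section 6.1.6 gives 4 mg dexamethasone twice daily as a ceiling. Table 7.2.4, for patients already on dexamethasone, gives the same dose as a floor.

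**The case against.** A reader might infer that suppressed responses will be reported as absence of immunogenicity. The documents do not support that. They plan no pooled responder rate and no conclusion of no immunogenicity, and a descriptive, graphical summary does not prevent anyone from marking steroid dose.

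A reader might also infer that patients treated for an NSC reaction will count as non-responders. That too goes too far. They have a recorded, graded clinical event. Section 6.1.5 asks for serum before supportive care where feasible, repeated about every two days, with the stored pre-treatment serum tested as well. Only grade 2 reactions lead to resumed NSC dosing on dexamethasone under Table 7.2.4. Nor can patients be assumed to be on 16 mg/day when sampled.

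The stakes are also limited. Stopping treatment depends on clinical signs rather than assay levels, and the recommended phase II dose rests on tolerated or feasible dose and toxicity. The numerical illustration rests wholly on assumed inputs. With all 29 anticipated patients, the chance of detecting at least one responder stays at 0.83 or above in the cases shown.

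All of this stands, and it narrows the point without removing it. The pre-steroid serum is for a cytokine panel, so it does not replace later T cell and antibody samples drawn on steroid. That an annotation is possible does not make it planned. A recorded clinical event does not tell a reader how to interpret a negative assay from the same patient.

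**Conclusion.** The point holds as a gap in analysis and reporting. The plan records corticosteroid dose but does not use it for T cell, antibody or titer results, so a negative or falling result on steroid is ambiguous. This affects what a key secondary objective can conclude. It does not affect the primary objective or any stopping decision.

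The size of any masking cannot be determined from the documents. The figures above show only that it could range from slight to substantial, depending on how many patients are on steroid at sampling and how strongly steroid reduces detection. The verdict rests on the omission and on the protocol's own handling of immunosuppression, not on those figures. It does not extend to a claim that the trial will report a false negative.

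**What to change.** In the synopsis Statistical Considerations and the Section 15 Analysis Plan, specify that:

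- each T cell, antibody and adenoviral titer result is listed and plotted with the corticosteroid dose at that draw;
- results on and off steroid are shown descriptively beside the overall summary;
- samples drawn after dexamethasone was started for a suspected NSC immune response are flagged;
- negative results obtained on steroid do not by themselves establish lack of immunogenicity.

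The cost is a few extra table columns from data already collected, and small strata. The on/off contrast should stay descriptive, since the reason for steroid use may itself relate to the immune response. No new sample, visit or treatment change is needed.

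Separately, Section 6.1.6 and Table 7.2.4 must be reconciled on the dexamethasone dose for an NSC immune response.
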